## 17.1. ROUTINE ADVERSE EVENT REPORTING

Adverse event data collection and reporting, which are required as part of every clinical study are done to ensure the safety of patients enrolled in the studies as well as those who will enroll in future studies using similar agents. AEs will be recorded as part of medical history during Screening. All adverse events that occur after the consent form is signed but before treatment allocation/randomization must be reported by the investigator if they cause the subject to be excluded from the study, or are the result of a protocol specified intervention, including but not limited to washout or discontinuation of usual therapy, diet, placebo treatment or a procedure. Any new AEs or increase of a documented AE from screening/history will be recorded from the time of the first treatment allocation/randomization through 30 days following cessation of treatment. Adverse events are reported in a routine manner at scheduled times according to the study calendar in Section 9. All adverse events are entered into the eCRF in Rave. The investigator will make every attempt to follow all subjects with non-serious adverse events for outcome.

Adverse events will not be collected for patients during the pre-screening period as long as that patient has not undergone any protocol-specified procedure or intervention. If the patient requires a blood draw, fresh tumor biopsy etc., the patient is first required to provide consent to the main study and AEs will be captured according to guidelines for standard AE reporting.

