	Other important medical events that may not result in death, not be life threatening, or not require hospitalization may be considered a serious adverse event when, based upon appropriate medical judgment, the event may jeopardize the subject and may require medical or surgical intervention to prevent one of the outcomes listed previously (designated above by a †).	
Duration	Record the start and stop dates of the adverse event. If less than 1 day, indicate the appropriate length of time and units	
Action taken	Did the adverse event cause Pembrolizumab to be discontinued?	

Relationship to study drug	
Did Pembrolizumab cause the adverse event? The determination of the likelihood that Pembrolizumab caused the adverse event will be provided by an investigator who is a qualified physician. The investigator's signed/dated initials on the source document or worksheet that supports the causality noted on the AE form, ensures that a medically qualified assessment of causality was done. This initialed document must be retained for the required regulatory time frame. The criteria below are intended as reference guidelines to assist the investigator in assessing the likelihood of a relationship between the test drug and the adverse event based upon the available information.
 
The following components are to be used to assess the relationship between Pembrolizumab and the AE; the greater the correlation with the components and their respective elements (in number and/or intensity), the more likely Pembrolizumab caused the adverse event (AE):
	
	Exposure	Is there evidence that the subject was actually exposed to Pembrolizumab such as: reliable history, acceptable compliance assessment (pill count, diary, etc.), expected pharmacologic effect, or measurement of drug/metabolite in bodily specimen?
	Time Course	Did the AE follow in a reasonable temporal sequence from administration of Pembrolizumab? Is the time of onset of the AE compatible with a drug-induced effect (applies to studies with investigational medicinal product)?
	Likely Cause	Is the AE not reasonably explained by another etiology such as underlying disease, other drug(s)/vaccine(s), or other host or environmental factors

Relationship to Pembrolizumab (continued)	The following components are to be used to assess the relationship between the test drug and the AE: (continued)	

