### 19.1. SAMPLE SIZE JUSTIFICATION

According to the findings from the phase III study studying topotecan vs CAV in the second-line treatment of SCLC patients and the phase III study comparing oral and intravenous topotecan, we expect a median PFS of 12 weeks for the control arm (C) and 20 weeks (a 67% increase) for the experimental therapy (E) in the pooled patient population with relapsed sensitive or refractory SCLC. Under the assumption of exponential survival time, it corresponds to a hazard ratio  $\lambda_E/\lambda_C = 0.60$ . Assuming an accrual rate of 4 randomized patients per month, it will take approximately 23 months to enroll 93 randomized patients (62 arm E and 31 arm C). With additional follow-up of 26 weeks (approximately 6 months) after the enrollment of the last patient, or approximately 86 events (59 arm E, 27 arm C), the study has approximately 82% power to reject the null hypothesis  $\lambda_E/\lambda_C = 1$  and accept the alternative hypothesis  $\lambda_E/\lambda_C < 1$  when the true  $\lambda_E/\lambda_C = 0.60$  using a stratified log rank test at a 1-sided significance level of 0.10.

Per above, eligible patients will be randomized with 2:1 allocation to two arms (E and C). The patients on arm C are allowed to receive pembrolizumab after progression. The final analysis is expected to take place 6 months after the last enrolled patient has been treated.

In the primary analysis, a stratified log rank test with equal weights over time will be used to test the PFS difference between two arms. As late treatment effect is often observed for immunotherapy, a weighted log rank test with Fleming-Harrington weights also will be used as a supplementary analysis to maximize the test efficiency for late treatment effect. More details can be found in the Analytic Method section.

Objective response rate (ORR) is a secondary endpoint. The sample size of the study is not determined by having adequate power to test ORR. With 62/31 patients on arm E/C, the study has approximately 82% power to differentiate  $ORR < 12\%$  versus  $ORR > 32\%$  at one-sided significance level of 0.10

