## 20. STATISTICAL ANALYSIS PLAN

The primary analysis will include all randomized patients but exclude ineligible patients or patients who cancel this study before receiving any protocol treatment.

The primary efficacy endpoint is PFS, which is defined as the time from the date of randomization to the date of earliest radiographic disease progression or death. If the subject does not experience radiographic disease progression or death, then the data will be censored at the date of the last disease assessment. PFS will be analyzed by Kaplan Meier methodology and compared between arm E and arm C, using a log-rank test stratified by disease type (sensitive vs refractory). A two-sided, stratified log-rank test P value will be provided. Median PFS time will be calculated and 95% confidence interval for median PFS will be presented. Overall survival (OS) will be analyzed in a similar manner as PFS.

Late treatment effect is often expected for immunotherapy. For this reason, a weighted log rank test with Harrington-Fleming weights that optimize the expected late treatment effect will be conducted as a supplementary analysis for both PFS and OS. In particular, the following three parameter settings will be used: (1)  $\rho = 0$  and  $\gamma = 0.5$ ; (2)  $\rho = 0$  and  $\gamma = 1$ ; and (3)  $\rho = 0$  and  $\gamma = 2$  (39).

The proportion of subjects with objective response as assessed by the investigator using RECIST version 1.1 will be evaluated for randomized subjects. The objective response rate will be estimated and compared between arm E and arm C, using a Cochran-Mantel-Haenszel (CMH) test stratified by tumor volume. A two-sided, stratified CMH test P value will be provided. In addition, a 95% confidence interval will be constructed for the estimated proportions. Similar analysis will be conducted for disease control rate (DCR), which is defined as the proportion of patients achieving complete, partial and stable disease after the protocol treatment.

All subjects who receive at least one dose of the study drug will be included in safety analysis. Treatment-related toxicity will be summarized by grade, type and system organ

class. Comparisons of the percentages of subjects experiencing an adverse event between arm E and arm C will be performed using Fisher's exact test.

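### Crude adverse-event percentages are compared by Fisher's exact test although, on the plan's own assumptions, randomized-treatment observation is about 1.4 times longer on pembrolizumab than on topotecan

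*Combined protocol and SAP*

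**What the plan says.** Section 20 defines the safety population: "All subjects who receive at least one dose of the study drug will be included in safety analysis". Toxicity is to be summarized by grade, type and system organ class, and then: "Comparisons of the percentages of subjects experiencing an adverse event between arm E and arm C will be performed using Fisher's exact test". No significance level or sidedness is stated for this comparison. The plan has no patient-time rate, no analysis of time to first event and no common observation window.

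The observation window is set elsewhere. Section 10.1 gives both drugs until progression or unacceptable toxicity, and the synopsis caps pembrolizumab at 24 months. Section 17.1 collects adverse events from randomization "through 30 days following cessation of treatment". Footnote 22 of Table 2 ends collection earlier if a new antineoplastic therapy starts. Section 19.1 supplies the expected durations: "we expect a median PFS of 12 weeks for the control arm (C) and 20 weeks (a 67% increase) for the experimental therapy (E"), under exponential survival. Arm C patients may receive pembrolizumab after progression. Section 20 does not say whether events after that crossover belong to arm C.

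**The concern.** The percentage of patients who ever had an event depends on how long they were watched. Treatment and event collection both follow progression, so the design's own expectation of longer PFS on pembrolizumab is also an expectation of a longer window in arm E. Fisher's test treats the two windows as equal. Two errors follow when arm C is observed on randomized treatment only: equal toxicity per week can look like excess pembrolizumab toxicity, and a higher weekly rate on topotecan can be hidden by its shorter exposure. Section 6.2 makes the safety and tolerability of pembrolizumab a secondary objective, and this is the only formal safety contrast that the plan offers.

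**Working it through.** **Reproducing the plan's figure.** The 20- and 12-week medians also drive the sample size, so that was checked first. Section 19.1 states "the study has approximately 82% power to reject the null hypothesis" "using a stratified log rank test at a 1-sided significance level of 0.10". Under the Schoenfeld formula, power = Φ(|ln HR|·√(d_E·d_C/d) − z). With HR = 12/20 = 0.60, d = 86 (59 E, 27 C) and z = 1.2816, this gives Φ(0.5108 × √(59 × 27/86) − 1.2816) = 82.0%. The stated figure is reproduced. The documents give no figure for the adverse-event comparison.

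**Inputs from the plan.** 62 E and 31 C; exponential medians of 20 and 12 weeks; accrual of 4 patients per month; 26 weeks of follow-up after the last patient; 24-month cap (applied to both arms in the model, negligible for C); 30-day tail.

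**Assumptions added here.** Treatment time equals PFS time; first events have a constant weekly hazard h; Fisher's test is two-sided at 0.05; arm C is observed on randomized treatment plus 30 days only.

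**Mean observation (weeks).**

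| Step | E | C | Ratio |
|---|---|---|---|
| Treatment, median/ln 2 | 28.9 | 17.3 | 1.67 |
| With 24-month cap, plus 30 days | 32.4 | 21.6 | 1.50 |
| Also truncated at the data cut | about 29 | about 21 | 1.41 |

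**Proportion with an event, equal hazard.** Without the cap and data cut, P = 1 − e^(−hw)·λ/(λ + h), where λ = ln 2/median and w = 30/7 = 4.29 weeks. At h = 0.03, e^(−hw) = 0.879.
- E: λ = 0.0347, so P = 1 − 0.879 × 0.0347/0.0647 = 53%.
- C: λ = 0.0578, so P = 1 − 0.879 × 0.0578/0.0878 = 42%.

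Applying the cap and the data cut gives 51% and 42%.

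**Fisher's test.** All tables for 62 v 31 were enumerated at these proportions. The test is significant in 13.6% of trials, 13.4% in the direction of more events on E. With both arms at C's proportion the total is 4.4%. At equal hazards of 1% and 5% per week it is about 8% and 13%.

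**Unequal hazard.** With topotecan at 4.5% per week and pembrolizumab at 3%, the proportions are C 53% and E 51%. Over arm C's own window, 3% per week gives 42% and 4.5% gives 53%, so a difference of about 11 points has been masked.

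**Where the effect shrinks or turns.**
- Rare events: with C at 5% or 10%, the gap is 2 to 4 points and the test is significant in under 5% of trials.
- Early events only: if first events can occur only within 6 to 12 weeks of starting, the gap is about 0 to 2 points with the 30-day tail at risk, and rejection stays near 3 to 5%. If the tail carries no risk, the gap is about 2 to 5 points.
- Post-crossover events counted in arm C: at 3% per week, with an assumed 50% crossing over for a median of 12 further weeks, C is about 51% against E 51%. With 70% crossing over, C is about 55%.

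**The case against.** The strongest reply is that the direction is not fixed by the documents. Crossover pembrolizumab is protocol treatment, Section 20 includes everyone who received a dose, and it compares the arms by their labels. A reader could therefore count post-crossover events in arm C, and the gap then closes or reverses. This stands, and the conclusion is limited accordingly. It does not rescue the planned comparison, because that reading balances the windows only by adding pembrolizumab toxicity to the topotecan arm.

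Second, the 14% rests on a hazard that never wanes, and the documents give no onset-time data. This also stands. However, Section 14.1.1 says that pembrolizumab events may arise soon after the first dose or months after the last, so an early-only pattern cannot be presumed.

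Third, the percentage with an event while treated to progression is a legitimate measure of total burden. It is, and it should be kept. It does not answer whether one drug is more toxic for the same time on treatment.

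Fourth, the stakes are modest. The safety objective is not worded as a comparison, no level is set, and Section 19.3 suspends accrual on separate counts among the first 20 patients per arm. All of this stands. A reader might infer that the trial would probably report false pembrolizumab toxicity. The figures do not support that: about 86% of trials would show no significant difference even in the 3% case.

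**Conclusion.** The point holds in conditional form. If arm C is observed on randomized treatment only, the plan's assumptions give windows of about 29 and 21 weeks, and nothing in the documents corrects for this. For common events with a steady, equal weekly hazard, the crude comparison shows an excess on pembrolizumab of about 10 points (51% v 42% at 3% per week). It also raises the chance of a significant Fisher result from about 4% to about 14%. A 1.5-fold higher topotecan hazard is nearly concealed.

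These figures rest on the planned medians, treatment time equal to PFS, a constant hazard and an assumed two-sided 0.05. A reader might infer that observation on pembrolizumab is far longer, or that the bias always runs against it. The documents support neither: the ratio is about 1.4, the effect is small for rare or early events, and its direction depends on a crossover attribution rule that Section 20 does not state. Priority is low to moderate.

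**What to change.** In Section 20:
- Keep the percentages by arm as a description of total burden.
- Make the between-arm comparison first-event incidence per patient-week, with a rate ratio and 95% CI. Time at risk runs from the start of randomized treatment to the earliest of first event, 30 days after the last randomized dose, first crossover dose, death and data cut.
- Alternatively, use time to first event over the same period, with death and treatment discontinuation handled explicitly as competing events.
- State that events after the first crossover dose are not attributed to arm C in this comparison, and tabulate them separately with their own time at risk.

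Under a constant hazard the rate ratio targets 1.00 when weekly toxicity is equal, and 1.5 (C to E) in the masked case. Precision will be limited. With about 32 E and 13 C patients having an event (0.51 × 62 and 0.42 × 31), the standard error of the log ratio is √(1/32 + 1/13) = 0.33. An estimate of 1.00 would then carry a 95% CI of roughly 0.52 to 1.9.

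The cost is SAP wording and a few table columns. Table 13 already requires sites to "Record the start and stop dates of the adverse event", and treatment is given at scheduled cycle visits, so the dates needed should be at hand. The downsides are that rates assume a roughly constant hazard and that stopping treatment may be informative. The time-to-event version avoids the first but not the second, so the handling of discontinuation should be written down in advance.

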Laboratory/Correlative Study Assessments	
Tumor samples will be required at study entry. Although subjects will be enrolled regardless of PD-L1 status, subjects will be required to provide tissue of a tumor lesion (either archived tissue if sample was obtained no more than 42 days prior to signing consent or a new biopsy before initiating therapy). Patients in the pembrolizumab arm will undergo a repeat biopsy while on treatment, if clinically feasible, during weeks four to six after initiating treatment. Those patients on the topotecan arm that progress and cross-over to receive pembrolizumab will undergo a biopsy, if clinically feasible, before initiating the new treatment.
 
Tissue-based correlative studies will be performed, including and not limited to, immunohistochemistry to evaluate expression of PD-L1 and immune cell markers, whole exome sequencing for evaluation of mutational burden and the neoantigen landscape, and transcriptome analyses of the tumor and immune microenvironment. Peripheral blood cell/serum/plasma samples for correlatives will be collected for all patients at screening, at week 4-6 biopsy, at imaging during all cycles, and at progression/cross-over for characterization of T-cell phenotypes to understand how changes may correlate with clinical response.

Study Follow-Up	
After the end of treatment, each patient will be followed for a minimum of 30 days for adverse event monitoring. Serious adverse events will be collected for up to 90 days after the end of treatment or 30 days after the end of treatment if the subject initiates new anticancer therapy, whichever is earlier. Subjects who discontinue treatment for reasons other than disease progression will have post-treatment follow-up every 6 weeks for disease status until progression, initiating a non-study cancer treatment, withdrawing consent, or becoming lost to follow-up. All subjects will be followed by telephone contact every 12 weeks for overall survival until death or withdrawal of consent.

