Although subjects will be enrolled regardless of PD-L1 status, subjects will be required to provide tissue of a tumor lesion (either archived tissue or a new biopsy before initiating therapy). Tumor samples will be required before initiating therapy (preferably a new specimen) and a repeat biopsy will be performed, if clinically feasible, on-treatment (during weeks 4 to 6) for those in the pembrolizumab arm and at the time of disease progression for those in the topotecan arm. PD-L1 expression status by immunohistochemistry will be determined on tumors at baseline, on treatment and at the time of topotecan progression. Numerous other correlative studies also will be performed, as outlined below. Peripheral blood mononuclear cell samples will be collected at screening, at day 1 of cycles 1, 2 and 3, and at the time of each imaging study (while on study), for characterization of T-cell phenotypes to understand how changes may correlate with clinical response.

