### 6.3. EXPLORATORY OBJECTIVES

- i. To describe the immunophenotype of SCLCs, assessed by immunohistochemistry and the associations with ORR, PFS and OS to each of the treatment arms.
  - a. For those patients treated in the pembrolizumab arm, pre-treatment samples also will be compared to on-treatment biopsy samples to identify the immunophenotype of response.
- ii. To describe the temporal change in T cell immunophenotypes in peripheral blood mononuclear cell samples and correlate with clinical response.
- iii. To explore the relationship between mutational burden and response to pembrolizumab therapy.
- iv. To identify candidate neoantigens and explore their associations with response to pembrolizumab therapy.
- v. To examine the changes in tumors that are associated with either response or resistance to study therapy by performing comparative analyses on matched specimens.

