-  Whole blood samples for genomic analyses, and peripheral blood cell/serum plasma samples for correlatives will be collected for all patients at screening, at week 4-6 biopsy, at imaging during all cycles, and at progression/cross-over. Samples will be collected per Section 12. Note that each time point requires differing types of blood collection. Please refer to the lab manual for detailed instructions on sample collection. § For patients who cross-over from the topotecan arm to the pembrolizumab arm, they will undergo the same assessments and procedures from study start, except that a repeat tumor biopsy will not be performed during weeks 4 to 6.

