### 13.4. PERIPHERAL BLOOD BASED STUDIES

Multiparametric flow cytometry will be performed at baseline and during treatment to assess baseline and changes in composition/activation status of lymphocyte subsets present in peripheral blood mononuclear cell preparations (PBMCs). Lymphocyte subsets to be assayed may include, but are not limited to CD3+, CD8+ and CD4+ T-cell subsets (activated; effector/memory; regulatory) and populations of those cells as defined by the expression of activation, exhaustion, or signaling markers such as, but not limited to, FoxP3, Ki67, ICOS, CTLA-4, PD-1, LAG-3, and Tim-3.

Serially collected PBMCs may also be used to screen for autologous neoantigen-specific T cell responses in the peripheral blood. Methods for doing so include combinatorial coding with peptide-MHC multimers, which permits high-throughput detection of antigen-specific T-cells to multiple potential antigens in parallel. Briefly, using synthesized peptides from candidate neoantigens as described above, large quantities of fluorochrome-labeled peptide-MHC complexes are generated such that each neoantigen is coded by a unique fluorochrome combination. Then, using conditional MHC ligands that are cleaved upon exposure to UV-light, empty, peptide-reactive MHC molecules are then exposed to autologous T-cells and reactivity of TILs to peptide-MHC complexes will be assessed and quantified by flow cytometry.

Neoantigen-specific T-cells will be isolated and may be expanded and used for future experiments.

As improvements in technology and scalability permit, alternative strategies for identifying neoantigen-specific T cells in treated patients may be explored.

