The association between candidate biomarkers in tumor samples, including, but not limited to, CD3, CD4, CD8, FoxP3, PD-1, CD68, MHC class I and II, and PD-L1, with response will be evaluated using Wilcoxon rank sum test. The association of these biomarkers with PFS and OS will be evaluated using single-predictor Cox models.

The correlation between T-cell immunophenotypes in peripheral blood mononuclear cell samples and clinical response will be evaluated with Chi-square test.

The correlation between mutational burden in tumor specimens and objective response will be evaluated using Wilcoxon rank sum test separately for patients treated by pembrolizumab and topotecan.

The difference in neoantigen signature between SCLC tumors responding to PD-1 inhibition and those not responding to therapy will be evaluated.

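### The chi-square test planned for serial blood T-cell measurements has no stated categories, time point or change measure; a Wilcoxon comparison of a prespecified change would serve the objective better at almost no cost

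*Combined protocol and SAP*

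**What the plan says.** Section 6.3 sets exploratory objective ii: "To describe the temporal change in T cell immunophenotypes in peripheral blood mononuclear cell samples and correlate with clinical response". Section 13.4 describes the assay: "Multiparametric flow cytometry will be performed at baseline and during treatment to assess baseline and changes in composition/activation status of lymphocyte subsets". The Synopsis gives the purpose of the serial blood draws as "for characterization of T-cell phenotypes to understand how changes may correlate with clinical response".

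The only analysis text for this objective is one sentence in section 20: "The correlation between T-cell immunophenotypes in peripheral blood mononuclear cell samples and clinical response will be evaluated with Chi-square test". It gives no categories, cut-points, time point, change measure, method for repeated samples or handling of treatment arm. Section 13.5 compares dynamics in responders and non-responders, but that concerns T-cell receptor sequencing and names no method.

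The neighboring sentences of section 20 proceed differently. Tumor biomarkers such as CD8 and PD-L1 are to be compared "with response will be evaluated using Wilcoxon rank sum test", and mutational burden by "Wilcoxon rank sum test separately for patients treated by pembrolizumab and topotecan".

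The sampling times are stated in two ways. Footnote 26 to Table 2, in agreement with the Synopsis, says that blood "will be collected for all patients at screening, at week 4-6 biopsy, at imaging during all cycles, and at progression/cross-over". Section 3.3.2 instead has samples at screening, "at day 1 of cycles 1, 2 and 3, and at the time of each imaging study".

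**The concern.** A chi-square test of association works on counts in categories. Subset composition and activation status from flow cytometry are quantitative, so someone must cut them, and the plan does not say where. That has three consequences. Information is lost in the cut. The cut-point can be chosen after the data are seen. And the sentence does not say whether the thing being cut is a baseline value, an on-treatment value or a change, although change is what the objective names and what the serial samples are drawn for.

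The plan also gives no reason for handling blood T-cell data differently from the tumor markers and mutational burden in the same section. At stake is whether the serial blood samples can answer the exploratory question for which they are collected.

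**Working it through.** The plan states no alpha, power or effect size for this analysis, so there is no figure to reproduce. The calculations below illustrate size only.

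**Inputs from the documents (section 19.1):** 62 pembrolizumab patients; response rates of 12% and 32%, which give 0.12 × 62 ≈ 7 and 0.32 × 62 ≈ 20 responders.

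**Assumed inputs:** all 62 patients have evaluable samples; normal values; responders shifted by 0.5 to 1.0 SD; two-sided 0.05; median split for the chi-square; 20% response (12 responders) as an intermediate case.

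**Large-sample efficiency under a normal shift.** Relative to the t-test, a median split has efficiency 2/π = 0.637 and Wilcoxon has 3/π = 0.955. Their ratio is 2/3, so a median split of 62 patients carries the information of about 62 × 2/3 ≈ 41.

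**Simulation.** With r responders and m non-responders, N = r + m:

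- Wilcoxon: z = (|U − rm/2| − 0.5) / √(rm(N+1)/12), reject if z > 1.96.
- Chi-square, uncorrected: X² = (k₁/r − k₀/m)² / [p(1−p)(1/r + 1/m)], reject if X² > 3.84. Here k₁ and k₀ count the values above the median and p = (k₁+k₀)/N.

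Rejection rates, Wilcoxon / median-split chi-square:

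| Responders of 62 | No shift (size) | 0.5 SD | 0.6 SD | 0.8 SD | 1.0 SD |
|---|---|---|---|---|---|
| 20 | 5.0% / 6.0% | 42% / 33% | 56% / 43–44% | 80% / 66% | 94% / 84% |
| 12 | 4.8% / 2.2% | 32% / 14% | – | 66% / 35% | 83% / 53% |
| 7 | 4.2% / 9.8% | 21% / 27% | – | 46% / 48% | 64% / 62% |

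Only the first row is close to like-for-like. With 12 responders the split test is conservative, so the gap overstates the information lost. With 7 it rejects about 10% of the time under the null, so its apparent power is inflated. An upper-quartile cut behaves differently again: at 0.8 SD it gives 58% with 20 responders and 60% with 12. The loss therefore depends on a cut-point that the plan does not state.

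**Why the time point and change measure matter.** Assume two samples per patient with within-patient correlation 0.5 to 0.7, and responders who differ only in the on-treatment sample, by 0.8 SD. A median-split chi-square on the baseline sample then rejects in about 6% of trials, which is no power. On the categorized change it rejects in 66% to 86%, and Wilcoxon on the change in 80% to 95%. If instead each patient's samples were entered in one table as though independent, the type I error at nominal 5% would be about 7–11% with two samples, 10–17% with three and 12–22% with four (correlation 0.3 to 0.7). The sentence in section 20 neither adopts nor excludes any of these analyses.

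**The case against.** The strongest reply is that silence is not a wrong method. Section 20 does not restrict the test to baseline, and a chi-square test of rise versus fall against response would serve objective ii. A reader might infer from the sentence that each patient contributes one value and that change over time goes untested. The documents support neither inference: they leave the matter open. What stands is that the link to change is not stated.

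It is also fair that the objective is partly descriptive, and description needs no test; that the word continuous does not appear and is inferred from the assay; and that the median split is an assumption of this check. The inference about the assay is a safe one for subset composition by flow cytometry, and any other cut would also have to be chosen.

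The power gap should not be read as a general result. The case with 20 responders uses the favorable response rate in section 19.1. With 7 responders the two tests look alike, though only because the chi-square exceeds its nominal size. Applying a continuity correction lowers the chi-square figure at 0.8 SD with 20 responders to about 44%, but the corrected test has a true size of only about 1%. Most of that further drop is conservatism rather than information lost, and the plan specifies no correction.

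Finally, for an exploratory analysis without alpha or a decision rule, the choice of test is partly preference. That limits the severity. It does not explain why a less informative test is used here alone among the quantitative markers.

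**Conclusion.** The point holds as a low-severity improvement. The planned chi-square test cannot be carried out without an unstated categorization, it discards information from quantitative measurements, and the text does not connect it to the change over time that the objective names. A Wilcoxon comparison, already used elsewhere in section 20, avoids the cut-point.

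The size is illustrative: about 12 to 14 points of power at 0.6 to 0.8 SD with 20 responders among 62 patients, under normality, a median split and two-sided 0.05. No dependable gap can be quoted when responders are few. The documents do not support saying that change over time is left untested, only that the plan does not say how it will be tested. The primary PFS conclusion and the ORR, OS and safety conclusions are unaffected.

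**What to change.** Replace the sentence in section 20 with a Wilcoxon rank sum comparison of responders and non-responders, separately for patients treated with pembrolizumab and with topotecan as for mutational burden. Apply it to (a) the baseline value and (b) the change from baseline to one prespecified on-treatment sample.

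- **Settle the sample first.** Reconcile section 3.3.2 with the Synopsis and Table 2 footnote 26, then name the sample, for example week 4–6 or first imaging. The week 4–6 biopsy is planned for the pembrolizumab arm only, so first imaging is the time point that both arms share.
- **Later samples.** Summarize them descriptively, or use a mixed model with a patient random effect, time and a response-by-time interaction. State that non-responders leave sampling early at progression, so later samples over-represent responders. Keep post-cross-over samples separate.
- **If categories are kept.** Fix the cut-points in advance, say whether they apply to a value or to a change, and use Fisher's exact test where cells are small.
- **Topotecan arm.** With 31 patients and 12% response there would be about 4 responders (0.12 × 31 = 3.7), and Wilcoxon power at 0.8 SD is only about 26%. Present that comparison as descriptive.

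The cost is a few SAP sentences and one reconciliation of sampling times, with no additional patients or assays.
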